patients (7 men and 8 women, mean age 62 years) who underwent OctreoScan with SPECT/CT of the chest for a clinical indication between the periods of April and November of 2013 at the University of Washington in Seattle. Most common clinical indication was detection of local and/or metastatic neuroendocrine tumors. Patients were injected with ~ 6 mCi of OctreoScan, and SPECT/CT of the chest was acquired 24 hr post-injection. OctreoScan uptake was semiquantitatively calculated using a target to blood pool ratio approach. Figure 2 depicts fused SPECT/CT images of how this was performed. Circular region of interests (ROI) of ~20 mm diameter were applied to left ventricular (LV) cavity blood pool (used as background, 2A and 2D), LV anterior (2B), inferior (2C), lateral wall (2E) and septum (2F), as well as the lungs (not shown), liver (2G), spleen (2G) and kidneys (2H). Results: Visually, the myocardium exhibited indistinguishable activity compared to the LV blood pool. However, there was significant LV regional differences in the uptake ratio/index as shown in **Table 1**. The inferior wall and septum showed higher (above blood pool) and the lateral and anterior walls lower (below blood pool) uptake ratios. This is most likely due to scatter emitted from the liver and spleen (Fig 2G) into the inferior wall (Fig 2C) and, to a lesser extent, the inferior portion of the septum. Likewise, identification of the septal wall (Fig 2F) was difficult given the lack of enough contrast definition on SPECT and CT images, for which an anatomical assumption was made, which makes ROI-based estimates less accurate at this location. These data demonstrated that under baseline conditions. OctreoScan uptake in the heart is indistinguishable from LV blood pool (~ 0.94 ± 0.17). These findings provide solid empirical basis for the work proposed in this project; the hypotheses are mechanistically plausible, clinically important, and testable.

d. Differences between OctreoScan and DOTATATE

There are important biological, technical, and practical differences between these radiopharmaceuticals that deserve a brief mention. Like indium-111 pentetrotide (Octreoscan®), 68-gallium dotatate has similar affinity for the same group of somatostatin receptors in inflammatory leukocytes (preferentially somatostatin receptor 2). The availability of 68-gallium dotatate provides several advantages, which are highly beneficial to the patients in this pilot study, including:

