- a. higher contrast and spatial resolution of PET/CT for detection of small lesions, which we think will result in improved sensitivity as compared to indium-111 pentetrotide SPECT;
- b. a nearly 75% reduction in the whole body effective radiation dose to patients from a single administration of gallium-68 dotatate (from 16.4 mSv for Octreoscan to 4.3 with Dotatate);
- c. convenience for patients and practical to perform. The entire gallium-68 dotatate PET imaging procedure takes ~2 hours in a single visit, compared to ~24 hours over 2 visits for octreoscan imaging.

II. SPECIFIC AIMS

Aim 1

To investigate if patients with clinically suspected cardiac sarcoidosis exhibit a myocardial OctreoScan or DOTATATE signal high enough (heart-to-blood pool ratio ≥ 2.0) to be visually detected compared to a control group of individuals (expected heart-to-blood pool ratio of ~ 1.0).

Sub-Aim1

To evaluate whether 4-hour (early) compared to 24-hour (delayed) post-OctreoScan injection imaging yields similar lesion detection performance.

Sub-Aim2

To correlate localization and number of increased radiotracer foci between FDG-PET and OctreoScan or between FDG-PET and DOTATATE studies.

Sub-Aim3

To explore the effect of treatment on DOTATATE activity in the heart on follow-up scans

III. SUBJECT SELECTION

We will enroll 30 adult subjects meeting the following inclusion/exclusion criteria.

a. Inclusion Criteria for initial study

- Individuals aged 18 or older

- Documentation of biopsy-proven sarcoidosis OR patients with typical findings on FDG PET and MRI without previous biopsy.

- Clinical suspicion of cardiac involvement defined as the presence of any of the following: high-degree A-V nodal block, complete bundle branch block, reduced left or right ventricular systolic function, any cardiac arrhythmia, and/or unexplained chest pain, dyspnea or syncope

- PET/CT imaging demonstrating abnormal myocardial FDG uptake consistent with active inflammatory myocardium.

b. Exclusion Criteria for initial study

-Initiation of steroids or any other immunosuppressive medication(s) following the completion of FDG-PET, as these medications, in theory, may subsequently suppress OctreoScan or DOTATATE uptake in the heart.

- Patients with history of neuroendocrine tumors (specially insulinomas)
- Patients taking the medication Octreotide
- Patients on total parenteral nutrition (TPN)
- Women who are pregnant or breastfeeding

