c. Inclusion Criteria for participation in follow-up study with Dotatate

- Initial dotatate PET scan consistent with active sarcoidosis. Defined as focally increased radiotracer activity in at least one left ventricular wall.

- Being on corticosteroid therapy at a dose of ≥ 10 mg/day of oral prednisone or equivalent for at least 6 weeks since initial dotatate PET scan.

IV. SUBJECT ENROLLMENT

Recruitment Procedures: Potential subjects will be recruited from the following sources: 1) Cardiomyopathy clinic; (2) Sarcoidosis clinic and 2) Nuclear Cardiology Laboratory.

Screening procedures will include daily or weekly queries for potential eligible subjects from lists of patients who have either undergone nuclear imaging or are scheduled to undergo imaging procedures for sarcoidosis. [name] will plan on educating the Nuclear Medicine Department staff about the study (recruitment information) as an additional way to ensure potential eligible patients are referred to the study. Our Nuclear Medicine Department staff will be instructed to notify [name] if they encounter an abnormal FDG-PET suggestive of active cardiac sarcoidosis, so that the study can be introduced by the nuclear technologists, physiologists or physicians before they leave the Nuclear Medicine facility.

If potential candidate is identified in the sarcoidosis clinic and/or cardiomyopathy clinic, patient's doctor or clinic staff will introduce the study to the patient. If patient is interested in learning more about the study, [name] will be notified, who will further discuss the study with the patient after the conclusion of his/her appointment with patient's doctor.

If potential patient is identified in the Nuclear Cardiology Laboratory the day of the patient's FDG PET scan, patient will be approached by one of the nuclear technologists, physiologists or physicians before they leave the Nuclear Medicine facility. Only non-study staff members may approach a potential patient in this manner. They can determine whether or not a patient may be interested in finding out more information and can refer him or her to the study team as appropriate. In this setting, the patient may be an inpatient or outpatient.

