Enrolled patients will be prospectively imaged after injection of either the radiotracer Indium-111 Penteotride (OctreoScan) or DOTATATE. We expect imaging 10 patients with OctreoScan and 20 patients with DOTATATE. No one will receive both radiotracer injections.

Patients will be scheduled for imaging Tuesday through Friday (no Mondays), since the dose of OctreoScan and DOTATATE must be requested by noon for next day delivery. Subjects will be advised to remain well hydrated prior to and for at least one day after tracer injection, this to reduce radiation exposure.

Women may participate in this study only if they are certain they are not pregnant. If the subject is a woman of childbearing age, a pregnancy test will be performed before OctreoScan or DOTATATE injection unless she has a history of total hysterectomy, is post-menopausal for more than 2 years or post-tubal ligation for more than 1 year.

OctreoScan Protocol

Visit 1 (Screening)

- Review the study with the subject and obtain written informed consent and HIPAA authorization.
- Assign the subject a unique study number.
- Record demographics data.
- Record medical history, including a history of biopsy-proven systemic sarcoidosis, diagnosis date, and prior treatments.
- Record concomitant medications.
- Schedule subject for Visit 2.

Visit 2 (Study Day 1)

- Subject arrives to the Nuclear Medicine Department.
- Concomitant medications review.
- Perform abbreviated physical examination.
- Perform and record vital signs.
- Place a peripheral intravenous (IV) line.
- Perform STAT quantitative serum hCG testing prior to each administration of Octreoscan
- Administer OctreoScan IV.
- Observe patient for 30 minutes post OctreoScan injection.
- Patient is to have a break and return to the Nuclear Medicine Department in 4 hours.
- Perform first set of images (~90 minutes)
- Subject can leave the Nuclear Medicine Department

[figure not shown]
Visit 3 (Study Day 2)

- Subject returns to the Nuclear Medicine Department 24 hours after OctreoScan injection
- Record any Adverse Experiences.
- Perform second set of images (~90 minutes).
- Subject has completed the study protocol at this point.

Follow Up

• All patients will be contacted by telephone at approximately 36-48 hours following the last scan for AE monitoring.

Figure 3. Example of Study Visits for OctreoScan Protocol

Study Day 1 (Approximately 6 hours)

Study Day 2 (Approximately 2 hours)

24 hours post	Whole Body	SPECT/CT	

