DOTATATE will be given intravenously at the dose of 4.0 mCi (148 MBq). They will then be observed for 60 minutes post DOTATATE injection at the nuclear medicine lab.

Cardiac acquisition: Individuals will be positioned with the help of a CT topogram (grid over the heart, level of the carina), and a low-dose CT scan (120 kVp, 20 - 30 mA) will be acquired for attenuation correction of PET emission data to cover the entire chest. This will be followed by a 20-minute ECG-gated 3-D PET acquisition of the chest and myocardium.

Imaging Processing:

All PET images will be reconstructed with attenuation correction (Matrix 128x128, OSEM, subsets 28, iteration 2, post filter 6.0 mm), and processed and reviewed using the vendor-supplied HERMES software package.

d. Data to be collected and when the data is to be collected

Visit 1. We will collect demographics data, medical history, prior treatments, and concomitant medications, as well as confirm a negative STAT quantitative serum hCG testing prior to the administration of Octreoscan or DOTATATE.

After visit 3 for OctreoScan or after visit 2 for DOTATATE we will analyze and interpret the images as following:

Image Interpretation for OctreoScan:

OctreoScan uptake in the heart will be assessed both qualitative and semi-quantitatively.

1. Qualitative Assessment of OctreoScan cardiac uptake: Two board-certified nuclear medicine physicians will review the early and delayed whole body planar and SPECT/CT images independently of each other and grade each image set based on OctreoScan uptake in the heart as: 1) negative, 2) borderline positive or 3) definitely positive. In this latter case, the number and location (relative to the left ventricular wall position) of positive lesions will be recorded. Similarly, FDG-PET studies (performed as part of the inclusion criteria) will be reviewed and the number and location of FDG-avid lesions recorded.

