We also believe that delayed imaging may lead to improved lesion detection performance due to a higher targetto-background ratio compared to early imaging.

Finally, we hypothesized that OctreoScan or DOTATATE will yield a similar number of abnormal cases (on a patient-basis) compared to FDG-PET.

VII. RISKS AND DISCOMFORTS

Radiation Exposure for OctreoScan Protocol:

1. The radiation dose patients will receive in this study is equivalent to an exposure of 16.4 mSv to the whole body (for one OctreoScan injection and two CT scans). This is more than the 3 mSv that the average person in the United States gets each year from natural sources like the sun, outer space, air, food and soil. It is less than the 50 mSv of radiation that is allowed each year for people who are exposed to radiation in their jobs. Although radiation may cause cancers at high doses and high dose rates, currently there are no data to establish unequivocally the occurrence of cancer following exposure to low doses and dose rates – below about 100 mSv. Therefore, the risks of low-level radiation exposure are not known but are thought to be very low.

Radiation risks are reviewed by the Radiation Safety Committee (RSC) at BWH. Subjects who may be pregnant will be excluded from this study, as radiation may cause physical or genetic damage to a fetus. Calculations are below:

Radionuclide	Activity Each	Compound and Method	# Administration	Total Whole-Body Dose
	Administration	of Administration	per Subject	per Administration
Indium-111	222 MBq (6 mCi)	Pentreotide	One	12 mSv^{17}

Type of exam	# Exams per subject	Total Whole-Body Dose per Exam
Low-dose CT for attenuation correction of the chest	Two	2.2 mSv

Total effective dose estimate = 16.4 mSv (total for study)

Radiation Exposure for DOTATATE Protocol:

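### Entry requires an abnormal FDG scan, so the FDG comparison can only estimate detection in FDG-positive patients; tracer foci are also recorded under a narrower rule than FDG foci

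*Combined protocol and SAP*

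**What the plan says.** - **Entry.** Section III.a lists among the inclusion criteria "PET/CT imaging demonstrating abnormal myocardial FDG uptake consistent with active inflammatory myocardium".
- **Comparator.** Section V.d (Image Interpretation for OctreoScan) says that the FDG studies done for inclusion will be reviewed and their lesions counted and located.
- **Hypothesis.** The closing sentence of Expected Results, in the Biostatistical Analysis section, is that "OctreoScan or DOTATATE will yield a similar number of abnormal cases (on a patient-basis) compared to FDG-PET". No margin, test or interval is attached.
- **Foci.** Sub-Aim 2 is "To correlate localization and number of increased radiotracer foci between FDG-PET and OctreoScan or between FDG-PET and DOTATATE studies". Statistical Methods repeats the intention to compare number and location but names no method.
- **Recording rule.** Both tracers are graded negative, borderline positive or definitely positive. After the last grade the text adds: "In this latter case, the number and location (relative to the left ventricular wall position) of positive lesions will be recorded". No grade filter is given for FDG.
- **Size.** Section V.a: "We expect imaging 10 patients with OctreoScan and 20 patients with DOTATATE". No patient receives both.
- **Wording close to a definition of abnormal.** Aim 1 refers to a "signal high enough (heart-to-blood pool ratio ≥ 2.0) to be visually detected". Section III.c describes an initial DOTATATE scan consistent with active disease: "Defined as focally increased radiotracer activity in at least one left ventricular wall". That wording governs entry to the follow-up scan only. Neither is linked to the three grades.

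**The concern.** A comparison of two imaging methods normally needs patients in whom the reference scan is negative as well as positive. Here the reference result is fixed by the entry rule. The tracer count can equal the FDG count or fall below it, but it has essentially no way to exceed it. A finding of a similar number could nevertheless be read as showing that the tracers perform like FDG in general. That matters because section I.a motivates the study partly by the poor specificity of existing imaging, FDG included, and this cohort cannot address specificity relative to FDG. Section VIII.b already describes preliminary DOTATATE uptake as comparable with FDG.

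At the level of foci, a tracer scan graded borderline contributes no foci under the visual rule, while faint FDG foci face no stated filter. A difference in number could then come from the recording rule and not from the tracer. The text also does not say whether readers see the FDG images before scoring the tracer scans, so agreement on location would be hard to interpret.

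**Working it through.** **Inputs.** Planned sizes: 10 OctreoScan and 20 DOTATATE (V.a), which sum to the 30 in section III. The plan gives no power calculation, expected detection rate or margin, so there is no further figure to reproduce.

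**Step 1: what the patient-level table can contain.**

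| | FDG abnormal | FDG not abnormal |
|---|---|---|
| Tracer abnormal | a | b |
| Tracer not abnormal | c | d |

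The entry rule makes b + d = 0, apart from any patient reclassified when the FDG scan is reviewed. No analysis of such reclassification is planned. The control series in section I.c (15 patients with OctreoScan for other indications) has no FDG scan described, so it does not fill the right-hand column. Hence:

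- specificity relative to FDG, d/(b + d), is 0/0 and cannot be estimated;
- extra detection, b, is 0 by construction;
- detection in FDG-positive patients, a/(a + c) = a/n, is the only estimable quantity.

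**Step 2: precision of a/n.** Exact (Clopper-Pearson) 95% limits for x of n are: lower = 2.5% quantile of Beta(x, n − x + 1); upper = 97.5% quantile of Beta(x + 1, n − x). When x = n, the lower limit is 0.025^(1/n) and the upper limit is 1.

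- n = 10: 0.025^(1/10) = 0.692
- n = 20: 0.025^(1/20) = 0.832

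The outcomes below are illustrative, not predictions.

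| Tracer | Detected | Proportion | Exact 95% CI |
|---|---|---|---|
| OctreoScan | 10/10 | 100% | 69.2% to 100% |
| OctreoScan | 9/10 | 90% | 55.5% to 99.7% |
| OctreoScan | 8/10 | 80% | 44.4% to 97.5% |
| DOTATATE | 20/20 | 100% | 83.2% to 100% |
| DOTATATE | 18/20 | 90% | 68.3% to 98.8% |
| DOTATATE | 16/20 | 80% | 56.3% to 94.3% |

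**Step 3: foci.** Let D be the tracer foci on definitely positive scans, B those on borderline scans, and F the FDG foci. The visual rule compares D with F; a like-for-like count would compare D + B with F. The shortfall is B. Its size cannot be computed because the documents give no expected number of borderline scans.

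The semi-quantitative OctreoScan step places a region on every visible left ventricular focus, with no grade filter, so part of B may be captured there. The DOTATATE step measures the peak area of each wall, also unfiltered, but on the slice with the highest uptake; that is not a count of foci. The text does not say that either step feeds the Sub-Aim 2 count.

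**Step 4: effect of the grade assignment.** One patient moved between abnormal and not abnormal shifts the proportion by 1/10 = 10 points (OctreoScan) or 1/20 = 5 points (DOTATATE).

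**The case against.** Four points on the other side deserve weight.

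1. **Enrolling FDG-positive patients is a reasonable first step.** In a pilot asking whether a signal is visible at all, it is sensible to start where disease is thought to be active. This stands in full; nothing here argues against the entry rule for Aim 1.

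2. **The plan does not claim equivalence.** A reader might infer a planned test of equivalence or agreement with FDG that is invalid by design. The documents do not support that. The sentence is an expectation without margin or test, the only planned kappa is between readers, and section VIII.b calls FDG the reference. What remains is that the wording invites a broader reading than the cohort can bear.

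3. **The primary endpoint may not be undefined.** A reader might infer this because no section supplied maps the grades to abnormal. That goes too far. The 2.0 ratio and the focal-uptake wording in section III.c are partial anchors, and the variable list sits in spreadsheet attachments that were not provided and could hold a definition. Borderline positive could also naturally be read as positive. The supported statement is that the protocol text does not say which grades count, how discordant reads are settled, or which OctreoScan time point is the main one.

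4. **The foci loss may be partial.** The unfiltered region-of-interest step stands as a mitigation, as set out in the working.

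It would also be too strong to say that scans already read were read with knowledge of FDG. Section VIII.b does not say who read them or how.

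**Conclusion.** The point holds in limited form. At patient level, the FDG comparison reduces to one detection proportion per tracer among FDG-positive patients, with a lower 95% limit no better than 69% (OctreoScan) or 83% (DOTATATE) at the planned sizes. It says nothing about specificity or added yield relative to FDG. At foci level, the stated visual rules are unequal between tracer and FDG and can bias tracer counts downward by an amount the documents do not allow one to size. The missing link between grades and abnormal is a matter of clarification, not a demonstrated flaw.

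This rests on three assumptions: that all listed inclusion criteria apply together, that review of the FDG scans reclassifies few or no patients, and that recruitment reaches 10 and 20. It should be corrected, but it does not undermine the pilot's main aim.

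**What to change.** 1. **Restate the hypothesis** in Expected Results as the proportion of FDG-positive patients with an abnormal tracer scan, separately for OctreoScan and DOTATATE, each with an exact 95% interval. Limit the conclusion to detection in FDG-positive patients.
2. **Record number and location of foci** on borderline as well as definitely positive scans, so that tracer and FDG foci are counted on the same basis.
3. **Set the reading order.** Have the existing readers score tracer scans before seeing the FDG images. For scans already read, report how they were read.
4. **Clarify abnormal in the protocol text.** State which grades count, reconciled with the section III.c wording and the 2.0 ratio, and give the other borderline assignment as a sensitivity analysis. Add a rule for discordant reads and name the main OctreoScan time point. The 24-hour image matches the control series, for which "SPECT/CT of the chest was acquired 24 hr post-injection". If the attachments already contain a definition, bring it into the text.

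Cost: wording, one recording rule and a reading order, with slightly more work per scan and no additional imaging or patients. Whether new data fields are needed cannot be judged without the attachments. The downside is a narrower claim about FDG.

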1. The radiation dose patients will receive in this study is equivalent to an exposure of 4.3 mSv to the whole body (for one dose of DOTATATE injection and one CT scan). This is more than the 3.0 mSv that the average person in the United States gets each year from natural sources like the sun, outer space, air, food and soil. It is less than the 50 mSv of radiation that is allowed each year for people who are exposed to radiation in their jobs. Although radiation may cause cancers at high doses and high dose rates, currently there are no data to establish unequivocally the occurrence of cancer following exposure to low doses and dose rates – below about 100 mSv. Therefore, the risks of low-level radiation exposure are not known but are thought to be very low.

Radiation risks are reviewed by the Radiation Safety Committee (RSC) at BWH. Subjects who may be pregnant will be excluded from this study, as radiation may cause physical or genetic damage to a fetus. Calculations are below:

Radionuclide	Activity Each	Compound and Method	# Administration	Total Whole-Body Dose
	Administration	of Administration	per Subject	per Administration
Gallium-68	148 MBq (4 mCi)	DOTA, Tyr ³ octreotate	One	3.1 mSv ²⁰

Type of exam	# Exams per subject	Total Whole-Body Dose per Exam
Low-dose CT for attenuation correction of the chest	One	1.2 mSv

Total effective dose estimate = 4.3 mSv (total for study)

For subjects participating in the OPTIONAL second DOTATATE scan, the total effective dose will be 8.6 mSv.

2. Side Effects: The following adverse effects have been observed in clinical trials using OctreoScan at a frequency of < 1% of 538 patients: dizziness, fever, flush, headache, hypotension, changes in liver enzymes, joint pain, nausea, sweating, and weakness. These adverse effects were transient in all cases.

According to the package insert, the safety of DOTATATE has been evaluated in three single center studies and in a survey of the scientific literature. No serious adverse reactions were identified, including a small study there were no observed adverse events to the radiopharmaceutical in the immediate or delayed time frames, with a follow-up of 1 year.²¹

3. Venous cathethers: Intravenous (IV) lines are required for OctreoScan or DOTATATE injection. Their placement may cause bruise, temporary clotting, bleeding, redness, swelling, and potentially infection at the insertion site. Some people may feel lightheaded or even faint during IV placement.

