- Results in congenital anomaly, or birth defect,

- Requires inpatient hospitalization or leads to prolongation of hospitalization (hospitalization for treatment/observation/examination caused by AE is to be considered as serious)
- Other medically important events

Medical and scientific judgment will be exercised in deciding whether expedited reporting is appropriate in other situations, such as important medical events that may not be immediately life-threatening or result in death or hospitalization but may jeopardize the subject or may require intervention to prevent one of the other outcomes listed in the definition above. These events, including those that may result in disability, will be considered serious.

Criteria for Causal Relationship to the Study Drug

Adverse events that fall under either "Possible" or "Probable" should be defined as "adverse events whose relationship to the study drugs could not be ruled out."

Causal relationship	Criteria for causal relationship
to the study drug	
Not Related	A clinical event, including laboratory test abnormality, with a temporal relationship to drug administration which makes a causal relationship improbable, and/or in which other drugs, chemicals or underlying disease provide plausible explanations.
Possible	A clinical event, including laboratory test abnormality, with a reasonable time sequence to administration of the drug, but which could also be explained by concurrent disease or other drugs or chemicals. Information on drug withdrawal may be lacking or unclear.
Probable	A clinical event, including laboratory test abnormality, with a reasonable time sequence to administration of the drug, unlikely to be attributed to concurrent disease or other drugs or chemicals, and which follows a clinically reasonable response on re-administration (re-challenge) or withdrawal (de-challenge).

Criteria for Defining the Severity of an Adverse Event

The following standard with 3 grades is to be used to measure the severity of adverse events, including abnormal clinical laboratory values.

- Mild: No disruption of normal daily activities
- Moderate: Affect normal daily activities
- Severe: Inability to perform daily activities

Reporting of Serious Adverse Events (SAEs)

In the case of a serious adverse event (SAE), the investigator will submit a report through eIRB within 5 working days/7 calendar days of the date the investigator first becomes aware of the problem as per Partners policy.

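### The adverse-event causality table puts a well-timed event with another plausible explanation in two categories, and a well-timed, otherwise unexplained event without challenge evidence in none

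*Combined protocol and SAP*

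**What the plan says.** All three definitions are in the combined protocol and SAP, Section IX.d, in the table under Criteria for Causal Relationship to the Study Drug.

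- *Not Related*: the event's timing is one "which makes a causal relationship improbable, and/or in which other drugs, chemicals or underlying disease provide plausible explanations".
- *Possible*: an event "with a reasonable time sequence to administration of the drug, but which could also be explained by concurrent disease or other drugs or chemicals". A second sentence adds: "Information on drug withdrawal may be lacking or unclear".
- *Probable*: reasonable timing, "unlikely to be attributed to concurrent disease or other drugs or chemicals", and in addition an event "which follows a clinically reasonable response on re-administration (re-challenge) or withdrawal (de-challenge").

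The text above the table pools *Possible* and *Probable* as "adverse events whose relationship to the study drugs could not be ruled out". *Not Related* events are outside that pool. There is no unclassifiable category and no order of precedence.

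On exposure, Section V.a plans 10 OctreoScan and 20 DOTATATE patients, none of whom receives both tracers. Section VII gives one OctreoScan injection per subject, and one DOTATATE injection with an optional second. Section III.c limits the second to patients with a positive first scan and at least 6 weeks of corticosteroid therapy since that scan.

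**The concern.** A causality scale has to place each event in exactly one category. This one fails in two places.

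First, the and/or makes an alternative explanation sufficient for *Not Related*, while the same feature, with reasonable timing, defines *Possible*. Two assessors who follow the table faithfully can code the same event differently, and one of them removes it from the pool of events not ruled out.

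Second, *Probable* makes a challenge response compulsory, which suits a drug given repeatedly better than a tracer injected once. The event that points most directly to the tracer, well timed and with no other likely cause, has no category unless challenge evidence exists.

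The overlap could well arise in this population. Section III.a admits patients with arrhythmia, conduction disease, ventricular dysfunction, or unexplained chest pain, dyspnea or syncope. Among the OctreoScan effects listed in Section VII are dizziness, hypotension and weakness, which cardiac disease can also cause. At stake is how consistently the study can say which adverse events might be tracer-related.

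**Working it through.** The plan has no figure to reproduce, because this is a classification rule. The check lists every combination of the features the table uses.

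**Features**
- T: timing is reasonable (T=1) or makes causality improbable (T=0).
- A: another plausible explanation exists (A=1) or is unlikely (A=0).
- D: a re-challenge or de-challenge response is shown (D=1) or not (D=0).

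**Rules as written**
- *Not Related* = (not T) or A
- *Possible* = T and A
- *Probable* = T and (not A) and D

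**Two alternatives**
- Reading and/or as plain *and*: *Not Related* = (not T) and A, the rest unchanged.
- Proposed wording: *Not Related* = not T; *Possible* = T and A; *Probable* = T and (not A).

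| T | A | D | As written | Read as *and* | Proposed |
|---|---|---|---|---|---|
| 1 | 1 | 1 | Not Related and Possible | Possible | Possible |
| 1 | 1 | 0 | Not Related and Possible | Possible | Possible |
| 1 | 0 | 1 | Probable | Probable | Probable |
| 1 | 0 | 0 | none | none | Probable |
| 0 | 1 | 1 | Not Related | Not Related | Not Related |
| 0 | 1 | 0 | Not Related | Not Related | Not Related |
| 0 | 0 | 1 | Not Related | none | Not Related |
| 0 | 0 | 0 | Not Related | none | Not Related |

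**Counts (one category / two / none)**
- As written: 5 / 2 / 1.
- Read as *and*: 5 / 0 / 3. The overlap goes, the hole stays, and events with improbable timing and no alternative explanation lose their category.
- Proposed: 8 / 0 / 0.

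**Who can supply D=1**
- Re-challenge: none of the 10 planned OctreoScan patients, since there is one injection and no crossover to the other tracer. For the 20 DOTATATE patients it depends on the optional second scan. Section IX.c discontinues subjects after a serious or intolerable event, so those reactions would not be re-challenged.
- De-challenge: an injected tracer cannot be withdrawn. The protocol does not say whether resolution after a single injection counts.

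**Scale, as illustration only.** If one event among 30 patients were coded out of the pool, the related-event proportion would move from 1/30 = 3.3% (exact 95% CI 0.1% to 17.2%) to 0/30 (0% to 11.6%; upper limit 1 − 0.025^(1/30) = 0.116). The plan does not say that it will compute this proportion.

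**The case against.** **The hole is softened by the note under *Possible*.** The remark that withdrawal information may be missing points an assessor without challenge data towards *Possible*, which is inside the pool. This stands as a guess about practice. It does not repair the definition, because the main clause still requires an event "which could also be explained by concurrent disease or other drugs or chemicals".

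**Resolution may count as de-challenge.** A reader might infer that no single-injection patient can ever have a *Probable* event. The documents do not support that as a flat statement. Section VII says the listed OctreoScan effects were transient in all cases, and Section IX.d follows events to resolution or until they can be characterised. If resolution counts, a transient reaction can be *Probable*. A reaction that does not resolve, or whose course is not recorded, would still have no category.

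**The safety conclusion is not shown to be biased.** A reader might also infer a systematic drift towards no related events. The overlap permits either coding, and nothing sends events in the hole to *Not Related*. Nor can most known tracer effects be put down to the heart. The OctreoScan list is "dizziness, fever, flush, headache, hypotension, changes in liver enzymes, joint pain, nausea, sweating, and weakness", and fever, flush, joint pain and liver-enzyme changes are not obvious results of arrhythmia or ventricular dysfunction. The list is also for OctreoScan alone, while 20 of the 30 planned patients receive DOTATATE.

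**Subject protection does not rest on this table.** Section IX.a has adverse effects reported to the IRB, and Section IX.d has serious events reported and all events followed up, none of it conditional on causality. The endpoints in the Biostatistical Analysis section concern uptake, and no related-event rate is planned. All of this stands and limits the importance of the point.

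**Conclusion.** The defect is real and limited. As worded, the three definitions are neither mutually exclusive nor exhaustive: two of eight feature combinations fall in two categories and one in none. Reading and/or as *and* does not cure this.

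The overlap follows directly from the wording. It requires reasonable timing; an event with improbable timing is *Not Related* only. The practical size of the hole depends on whether resolution after one injection counts as de-challenge, which the protocol leaves open.

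The check assumes that reasonable and improbable timing are complements, and that the alternative explanation in *Not Related* is the same feature as in *Possible*. One could hold that the first is meant to be stronger than the second, but the table does not say so.

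The consequence is confined to the classification of adverse events and the count of those whose relationship could not be ruled out. A bias towards no related events is a risk that the overlap allows, not a demonstrated effect. No efficacy endpoint, sample size, error rate or reporting duty changes.

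**What to change.** Reword the table in Section IX.d so that each event has one category:

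- *Not Related*: the timing makes a causal relationship improbable.
- *Possible*: reasonable timing, with a plausible alternative explanation.
- *Probable*: reasonable timing, with an alternative explanation unlikely. Re-challenge or de-challenge information supports the judgement but is not required.

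Add one sentence on how de-challenge is understood for a single injection, in particular whether resolution counts. Simply changing and/or to *and* is not enough: even with the challenge condition dropped from *Probable*, events with improbable timing and no alternative explanation would have no category.

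The cost is an edit to one table and to any data-collection form that uses it; the documents at hand do not show such a form. The downside is small: a few more events may be listed as not ruled out.
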